#### 7.13 Maintenance (Cycles 4 and Beyond, or cycle 6 and beyond as the case may be for that patient)

- All patients will be initiated on maintenance therapy as below within 14 days of completing Day 100 visit post-SCT.

Agent	Dose	Route	Day	Cycles
Daratumumab	16 mg/Kg* (IV) 1,800 mg (Injection)	IV or Injection	1	Cycle 4-15 (or 6-17)
Lenalidomide	10 mg*	PO	1-21	Cycle 4-15

				(or 6-17)
--	--	--	--	-----------

Cycles 4-15 (or 6-17) length = 28 days

\*Any dose-adjustments will be made as per the prescriber information.

Daratumumab administrations as per prescriber information and institutional guidelines.

Note: Thromboprophylaxis is required as standard of care (see Section 9.3) for all patients on maintenance treatment.

- **NOTE:** Prior to Cycle 16 (or 18), patients who are still maintaining response will proceed to maintenance with single-agent daratumumab every 3 months till disease progression or unwanted adverse events, if any. Cycles 16 and beyond length = 90 days (3 months).
- In the event of disease progression, intolerable adverse event or patient refusal for continued therapy, they will proceed to event monitoring without any additional anti-MM therapy.
- Considering that there are newer immunotherapy compounds being made available for the treatment of multiple myeloma, based on the initial results of this clinical trial, amendments may be put in place to add more arms to the study with newer, proven safe combination regimens, especially for maintenance treatment.

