**ALERT:** **ADR reporting may be required for some adverse events (See Section 10)**

#### 8.1 General Considerations:

- Missed doses for lenalidomide are to be omitted rather than made up, unless the dose was forgotten and remembered on the same day, in which case the dose can be taken

that day. Any doses missed on a particular day are not to be made up the next day. Doses that are considered to be vomited are not to be made up and a mention about the time of dose and time of vomiting episode should be made in the pill diary.

- b) Daratumumab may be administered within  $\pm 1$  day of the scheduled dose if there are any logistical challenges (holiday, patient transport or other logistics, scheduling availability, etc.)
- c) If multiple toxicities are experienced, dose modifications will be based on the toxicity requiring the largest dose reduction.
- d) Reductions are based on the dose given in the preceding cycle and are based on toxicities with an attribution of possible, probable, or definite that were observed since the prior toxicity evaluation.
- e) If a drug is omitted due to specific adverse events and the patient is on combination therapy (maintenance therapy), the other agents, considered unrelated to the adverse event may be continued.
- f) If a patient cannot be administered a dose of daratumumab during Consolidation 1 (Cycles 1-2 or 1-4, as the case may be for that patient) for  $>28$  days due to adverse events or any other reason, the patient should be removed from the study treatment and go to event monitoring. (NOTE: Patients on maintenance therapy (cycles 4 and beyond, or cycle 6 and beyond as the case may be for that patient) may be continued on treatment with single-agent daratumumab or lenalidomide in case the other agent has to be permanently discontinued in absence of disease progression. If a patient on maintenance treatment must discontinue both, lenalidomide and daratumumab, they should be removed from the protocol therapy and proceed to event monitoring.

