## 8.2 Lenalidomide Dose Modifications

Lenalidomide (Days 1-21)	
Starting dose	10mg
-1	5 mg
-2	Discontinue

→ → Use the NCI Common Terminology Criteria for Adverse Events (CTCAE) version 4.0\*  
unless otherwise specified ← ←

CTCAE System/Organ/Class (SOC)	ADVERSE EVENT	AGENT	ACTION**

CTCAE System/Organ/Class (SOC)	ADVERSE EVENT	AGENT	ACTION**
Investigations	Platelet count decreased Grade 4	Lenalidomide	
*Omit dose until AE has resolved to Grade 1 or better
 
 
• Follow CBC weekly
 
• If thrombocytopenia <math><30,000/\text{mm}^3</math> recurs, reduce dose by one dose level (by 5 mg) and continue therapy when platelet count <math>\geq 30,000/\text{mm}^3</math>
 
 
If, after lenalidomide has been omitted, and the AE does not return to <math>\leq</math>Grade 1 within 4 weeks, then the patient may continue on single-agent daratumumab till the completion of maintenance and then proceed to Event Monitoring

	Neutrophil count decreased Grade 4		
*Omit dose until AE has resolved to Grade 2 or better
 
 
• Follow CBC weekly
 
* If neutropenia has resolved to <math>\leq</math>Grade 2, resume dose at one level lower
 
* If, after lenalidomide has been omitted, and the AE does not return to <math>\leq</math>Grade 1 within 4 weeks, then the patient may continue on single-agent daratumumab till the completion of maintenance and then proceed to Event Monitoring
 

Blood and lymphatic system disorders	Anemia Grade 4		
*Omit dose until AE has resolved to Grade 2 or better
 
 
• Follow CBC weekly
 
* If anemia has resolved to <math>\leq</math>Grade 2, resume dose at one level lower
 
* If, after lenalidomide has been omitted, and the AE does not return to <math>\leq</math>Grade 1 within 4 weeks, then the patient may continue on single-agent daratumumab till the completion of maintenance and then proceed to Event Monitoring
 

	Febrile neutropenia $\geq$ Grade 3		
 
• Omit dose and follow CBC weekly
 
• If neutropenia has resolved to <math>\leq</math>Grade 2, resume dose at same level with GCSF support (See Section 9.6)
 

CTCAE System/Organ/Class (SOC)	ADVERSE EVENT	AGENT	ACTION**

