Cardiac disorders	Sinus bradycardia/ other cardiac arrhythmia Grade 2	Lenalidomide	Omit dose and follow at least weekly until resolution • If AE resolves to $\leq$ Grade 1, reduce dose by one dose level (by 5mg) and continue therapy
	$\geq$ Grade 3		• Discontinue study treatment and go to event monitoring
Vascular disorders	Thromboembolic event $\geq$ Grade 3		• Omit dose and start anticoagulation; restart at investigator's discretion (maintain dose level)
Immune system disorders	Allergic reaction Grade 2-3		• Omit dose and follow at least weekly until resolution • If AE resolves to $\leq$ Grade 1, reduce dose by 5 mg and continue therapy
	Anaphylaxis Grade 4		• Discontinue study treatment and go to event monitoring
Skin and subcutaneous tissue disorders	Erythema multiforme $\geq$ Grade 3		Discontinue study treatment and go to event monitoring
	Skin ulceration $\geq$ Grade 2		Discontinue study treatment and go to event monitoring
	Other: Non-blistering rash Grade 3		• If Grade 3 omit dose and follow weekly until resolution • If AE resolves to $\leq$ Grade 2 continue therapy
	Other: Non-blistering rash Grade 4		• Discontinue study treatment and go to event monitoring
Other AEs	Non-hematologic AE assessed as related to lenalidomide $\geq$ Grade 3		• Omit dose and follow at least weekly until resolution • If the AE resolves to $\leq$ Grade 2, implement one dose reduction step and continue therapy (per Table 8.2)

\* Located at [http://ctep.cancer.gov/protocolDevelopment/electronic\\_applications.ctc.htm](http://ctep.cancer.gov/protocolDevelopment/electronic_applications.ctc.htm)

\*\* Use the following to describe actions in the Action column:

- Omit = The current dose(s) for the specified drug(s) during a cycle is skipped. The patient does not make up the omitted dose(s) at a later time
- Hold/Delay = The current dose(s) of all drugs during a cycle is delayed. The patient does make up the delayed dose(s) when the patient meets the protocol criteria to restart drugs.
- Discontinue = The specified drug(s) are totally stopped.

If lenalidomide has been omitted and the toxicity does not return to  $\leq$ Grade 2 within 28 days during Consolidation 1 (Cycles 1-2), may continue on single-agent daratumumab till the completion of maintenance and then proceed to Event Monitoring.

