**unless otherwise specified ← ←**

CTCAE System/Organ/Class (SOC)	ADVERSE EVENT	AGENT	ACTION**
Investigations	Neutrophil count decreased Grade 4 lasting >7 days	Daratumumab	Hold (Day 1) or Omit (Days 8, 15, or 22) Daratumumab ** until recovery to Grade ≤2 or baseline May restart at same dose at the next planned dosing date.
	Platelet count decreased Grade ≥3 with bleeding		
Blood and lymphatic system disorders	Febrile neutropenia ≥Grade 3		Hold (Day 1) or Omit (Days 8, 15, or 22) Daratumumab ** until recovery to Grade ≤2 or baseline May restart at same dose at the next planned dosing date.
	Neutropenia with infection, of any grade		
Gastrointestinal disorders	Nausea Grade 2 (if persistent for >7 days despite optimal antiemetic therapy)		Hold (Day 1) or Omit (Days 8, 15, or 22) Daratumumab ** until recovery to Grade ≤1 or baseline May restart at same dose at the next planned dosing date.
	Vomiting ≥Grade 3 (if persistent for >7 days despite optimal antiemetic therapy)		
	Diarrhea ≥Grade 3 (if persistent for >7 days despite optimal anti-diarrheal therapy)		
Other (Non-hematologic)****	Any other Grade 4 AE or any unmanageable Grade 3 AE that was present at baseline or lasts for >7 days after the last administration of daratumumab		Hold (Day 1) or Omit (Days 8, 15, or 22) Daratumumab ** until recovery to Grade ≤1 or baseline May restart at same dose at the next planned dosing date.

Additional Adverse Events:

\*\* If Daratumumab is omitted in the middle of the cycle and the toxicity resolves, patient can re-start the drug but the days of drug treatment missed do not need to be caught-up and can be omitted in order to maintain the cycle schedule.

- Dose omission: Daratumumab may be omitted for adverse event considerations for a maximum of 28 consecutive days during Consolidation 1 (Cycle 1-2 or 1-4, as the case may be for that patient). Patients on maintenance therapy may be continued on treatment with single-agent daratumumab or lenalidomide in case the other agent has to be permanently discontinued in absence of disease progression. If a patient on maintenance treatment must discontinue both,

lenalidomide and daratumumab, they should be removed from the protocol therapy and proceed to event monitoring.

- If multiple adverse events are seen, administer dose based on the greatest reduction required by any single adverse event observed.

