- Dose modifications are for adverse events attributed to study treatment only. Dose modifications are not required for adverse events if they are deemed unrelated and/or unlikely related to study treatment.
- Reductions apply to treatment given in the preceding cycle and are based on adverse events observed since the prior dose.

\*\*\*\* If cough, dyspnea, and other pulmonary symptoms occur, a chest x-ray and high-resolution chest CT scan should be obtained. Incentive spirometry studies (to include DLCO) should be considered. Consider Pneumocystis pneumonia or viral pneumonitis. Patients who experience a deep vein thrombosis (DVT), pulmonary embolus (PE), or other clotting event should have all study drugs temporarily omitted while full-dose anticoagulation is initiated (other than warfarin or other Vitamin K antagonist). There should not be a delay of more than 28 days in reinitiating the study treatment.

**NOTE:** If the patient experiences a significant adverse event requiring a dose reduction at the start of the next cycle, then the dose will remain lowered for that entire remaining length of the study treatment.

**NOTE:** In the event patient is benefitting from treatment and the delay was unrelated to treatment toxicity, patient may remain on study with approval of study PI.

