13.3 Criteria for Initiation of Event Monitoring

Patients who go off protocol treatment for the following reasons will go to the event-monitoring phase per Section 4.2:

- Progressive multiple myeloma at any time on the clinical trial
- Patient requests to discontinue study treatment
- Patient develops an intercurrent illness that precludes further participation, or requires a prohibited concomitant treatment
- The Investigator withdraws the patient in the patient's best interests
- Administrative reasons (e.g., the patient is transferred to hospice care)
- An adverse event, which in the opinion of the Investigator, precludes further trial participation
- A dose omission of more than 28 days beyond the scheduled date of retreatment for daratumumab or lenalidomide

All attempts should be made to complete the End of Study procedures if a patient goes off treatment early.

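### Section 13.3 lists a long omission of either drug as a reason for leaving protocol treatment, while Section 8 lets a maintenance patient stay on the other drug; nothing says which rule governs

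*Combined protocol and SAP*

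**What the plan says.** Section 13.3, headed as criteria for starting event monitoring, lists the reasons for which patients go off protocol treatment. The last is "A dose omission of more than 28 days beyond the scheduled date of retreatment for daratumumab or lenalidomide". It names no treatment phase and makes no single-agent exception.

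For maintenance, Section 8 says the following.

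- 8.1(e): when one drug of the combination is omitted for an adverse event, "the other agents, considered unrelated to the adverse event may be continued". No time limit is given.
- 8.1(f): the 28-day daratumumab limit applies to Consolidation 1. In maintenance either drug may be continued alone, and the removal rule is "If a patient on maintenance treatment must discontinue both, lenalidomide and daratumumab, they should be removed from the protocol therapy".
- 8.2, platelet, neutrophil and anemia rows: if lenalidomide has been omitted and the event has not recovered to Grade 1 or better within 4 weeks, "then the patient may continue on single-agent daratumumab till the completion of maintenance and then proceed to Event Monitoring". The febrile neutropenia row has no such text.
- 8.3: its 28-day cap is again limited to Consolidation 1, and "Patients on maintenance therapy may be continued on treatment with single-agent daratumumab or lenalidomide in case the other agent has to be permanently discontinued".

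The closing sentence of 8.2 deals with lenalidomide toxicity that does not recover "within 28 days during Consolidation 1 (Cycles 1-2), may continue on single-agent daratumumab till the completion of maintenance". A note at the end of 8.3 allows an exception where "the delay was unrelated to treatment toxicity, patient may remain on study with approval of study PI".

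**The concern.** Two parts of the protocol give different answers for a maintenance patient whose lenalidomide is held for more than 28 days. Under 13.3 the patient appears to leave protocol treatment; under Section 8 the patient may continue daratumumab. A patient who is still responding could therefore lose daratumumab only because the other drug was held, depending on which section the treating team follows.

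Secondary objective 2.21, the MRD-negative rate after 1 year of maintenance, is also exposed. Its marrow is scheduled before Cycle 16 (18). A patient in event monitoring has no scheduled marrow: the table in 4.2 lists none, and neither does the end-of-treatment column in 4.1. Section 16.42 nevertheless divides by all evaluable patients, so the removed patient counts in the denominator and cannot be a success without a marrow. The same patient kept on daratumumab would have the marrow.

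**Working it through.** **Where the two rules meet.** Section 7.11 gives daratumumab alone in Consolidation 1. Section 7.13 gives lenalidomide on Days 1-21 of Cycles 4-15 (6-17). The lenalidomide part of the 13.3 bullet can therefore operate only in the phase where Section 8 allows single-agent continuation.

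| Situation in maintenance | Section 13.3 | Section 8 |
|---|---|---|
| One drug omitted for a long time | Listed reason for leaving treatment after more than 28 days | 8.1(e): the unrelated drug may continue, no time limit |
| Lenalidomide omitted; platelets, neutrophils or anemia not recovered at 4 weeks | As above | 8.2: daratumumab may continue to the end of maintenance |
| One drug permanently discontinued | Arguable: a stopped drug has no scheduled retreatment date | 8.1(f), 8.3: the other drug may continue |
| Both drugs discontinued | Event monitoring | 8.1(f), 8.3: event monitoring |
| 8.2 row orders study treatment discontinued (e.g. Grade 4 anaphylaxis) | Event monitoring | Event monitoring |

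The first two rows conflict, the third is arguable, and the last two agree.

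**Could 13.3 simply cap the 8.2 permission?** That permission starts after 4 weeks, which is 4 × 7 = 28 days from the first omitted dose. The 13.3 limit can be counted in two ways:

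- From the first omitted dose, it is passed at 29 days, 29 − 28 = 1 day after the permission starts.
- From Day 1 of the next cycle, it is passed 8 + 29 = 37 days after a first omission on Day 21, or 28 + 29 = 57 days after one on Day 1. That is 37 − 28 = 9 to 57 − 28 = 29 days after the permission starts.

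A permission meant to run to the end of maintenance would thus lapse within 1 to 29 days. Treating 13.3 as a cap nearly empties the 8.2 text.

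**When the rules can collide before the 1-year marrow.** Set Cycle 4 Day 1 as day 0; Cycle 16 Day 1 is then 12 × 28 = day 336. Take a lenalidomide omission that does not end.

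- Counting from the first omitted dose: the latest Cycle 14 start (Day 21 = day 300) passes the limit at 300 + 29 = day 329, before 336. A Cycle 15 Day 1 start (day 308) passes at day 337, after it. Omissions starting in Cycles 4-14 qualify, 11 of 12 cycles.
- Counting from the next cycle's Day 1: a Cycle 13 start passes at 280 + 29 = day 309. A Cycle 14 start passes at 308 + 29 = day 337. Cycles 4-13 qualify, 10 of 12.

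For patients given the optional cycles, add two to each cycle number. These counts show when a collision is possible. They say nothing about how often it happens.

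**Size per patient.** Each removed patient who would have been MRD negative lowers the 1-year rate by 1/45 = 2.2 points at the planned 45 evaluable patients, or 1/20 = 5.0 points at the stated minimum of 20. As an assumed illustration, 29/45 = 64.4% (exact 95% CI 48.8 to 78.1) becomes 28/45 = 62.2% (46.5 to 76.2). The documents give no rate of single-drug stopping, so no total effect is calculated.

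**The case against.** The strongest reply is that 13.3 orders nothing. Its lead-in says where patients go once they are off treatment for a listed reason, and Section 8 may be what decides who goes off. Section 13.1 supports this, since responding patients continue treatment per protocol. This has weight, and a reader who infers automatic removal from 13.3 goes further than its words. It does not remove the problem: the section is headed as criteria, it names lenalidomide, and 13.1 only points back to the protocol without ranking its sections.

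A second reply is that 8.2 defines omission and discontinuation separately, and the 13.3 bullet concerns omission measured from a scheduled date. That softens the clash with the permanent-discontinuation text of 8.1(f) and 8.3. One might read the three 8.2 rows in the same way, since lenalidomide has in effect ended there, but those rows speak of a drug that has been omitted, as does 8.1(e). Prolonged omission remains a clear overlap.

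Other text does not settle it. The exception at the end of 8.3 covers only delays unrelated to toxicity, whereas the conflict arises chiefly from toxicity. The clotting-event instruction there concerns all study drugs held together. The closing sentence of 8.2 refers to a phase in which no lenalidomide is given.

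A reader might also see a contradiction in 7.13, where after "intolerable adverse event or patient refusal for continued therapy, they will proceed to event monitoring without any additional anti-MM therapy". That wording can mean intolerance of the whole regimen or of the later single agent, so it is ambiguous rather than contradictory.

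**Conclusion.** The inconsistency is real but limited. It is clear for prolonged omission of one drug in maintenance under 8.1(e) and the three 8.2 rows, and arguable for permanent discontinuation. With no stated precedence, the same event can lead to different management.

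The statistical effect falls mainly on one descriptive secondary rate, at 2.2 points per affected patient with 45 evaluable. This assumes that the patient would have been MRD negative and has no marrow after removal. Removal could also bring forward subsequent myeloma therapy, which 16.42 censors for PFS; that effect is possible but cannot be sized, and the PFS and OS definitions are unchanged.

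Two larger readings are not supported. The 10 or 11 of 12 cycles might suggest a frequent problem, but they describe opportunity only. The Day 100 primary endpoint is assessed before maintenance starts and is untouched. The point is worth correcting because it governs whether patients stay on active treatment and the correction is cheap.

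**What to change.** Keep the opening and the 28-day limit of the last bullet in 13.3, and replace its reference to the drugs with: *daratumumab in Consolidation 1, or all study drugs being given in maintenance; a maintenance patient who omits or discontinues only one drug may continue the other as permitted in Section 8, except where 8.2 requires discontinuing study treatment.*

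Separately, correct the reference to Consolidation 1 (Cycles 1-2) in the closing lenalidomide sentence of 8.2, because no lenalidomide is given in that phase.

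No change to 7.13 or 16.42 is needed. The cost is two short text edits, which could go into Amendment 9, listed as pending in the document history. No visits, tests or patients are added.

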13.4 Criteria for Study Discontinuation

The study may be temporarily or permanently discontinued at any site and at any time. Reasons for study discontinuation may include, but are not limited to, the following:

- Safety concerns
- Poor enrollment

- Non-compliance with the protocol, Good Clinical Practice guidances or other regulatory requirements by the Investigator(s)
- Request to discontinue the trial by a regulatory or health authority or an IRB
- Manufacturing difficulties/concerns

All Investigators and the requisite regulatory authorities will be notified if the study is suspended or terminated for safety reasons. In the case of such termination, the Investigator will notify the IRB.

#### 13.5 Ineligibles

A patient is deemed *ineligible* if after registration, it is determined that at the time of registration, the patient did not satisfy each and every eligibility criteria for study entry. The patient may continue treatment off-protocol at the discretion of the physician as long as there are no safety concerns, and the patient was properly registered. The patient will go directly to the event-monitoring phase of the study (or off study, if applicable).

- If the patient received treatment, all data up until the point of confirmation of ineligibility must be submitted. Event monitoring will be required per the protocol.
- If the patient never received treatment, on-study material and the End of Active Treatment/Cancel Notification Form must be submitted. No further data submission is necessary.

#### 13.6 Major violation

A patient is deemed a *major violation*, if protocol requirements regarding treatment in cycle 1 of the initial therapy are severely violated that evaluability for primary end point is questionable. All data up until the point of confirmation of a major violation must be submitted. The patient will go directly to the event-monitoring phase of the study. The patient may continue treatment off-protocol at the discretion of the physician as long as there are no safety concerns, and the patient was properly registered. Event monitoring will be required per Section 4.2 of the protocol.

